3.3. DOSING

3.3.1. Dosing Regimen

The dosing regimen will be a single dose treatment injection of RZL-012 in multiple sites.

Six subjects in cohort 1, all assigned to the RZL-012 treatment group will be dosed at a maximal dose of 40 mg RZL-012 (approximately 1/6.25th the NOAEL as determined in the GLP toxicology study). Dosing will be calculated according to the size of the nodule (diameter) as determined by ultrasound in a dose of 5mg/cm²:

Nodule of 2-2.9cm diameter, as determined by ultrasound, will be injected 2 injections (0.1 mL each, 1 cm apart); total of 10 mg RZL-012.

Nodules of 3-3.9cm diameter, as determined by ultrasound, will be injected 3 injections (0.1 mL each, 1 cm apart); total of 15 mg RZL-012.

Nodules of 4-8cm diameter, as determined by ultrasound, will be injected 4 injections (0.1 mL each, 1 cm apart); total of 20 mg RZL-012.

Cohort 1 – Dercum's disease			
Number of Subjects – Active	6		
Nodule size – diameter (cm)	2-2.9	3-3.9	4-8
Total Dose of RZL-012 (mg)	10	15	20
Dose per NOAEL*	1/25 th	1/18.75 th	1/12.5 th
Number of Injections	2	3	4

Six subjects in cohort 2, all assigned to the RZL-012 treatment group, will be dosed as follows:

The first 3 subjects will receive 30mg RZL-012 in 6 injections (0.1mL each) in one leg followed by 30mg RZL-012 (6 injections, 0.1mL each) in the second leg adding up to 12 injections of 60mg RZL-012 (1/4.688th the NOAEL based on HED from GLP toxicology study).

The last 3 subjects will receive 40mg RZL-012 in 8 injections (0.1mL each) in one leg followed by 40mg RZL-012 (8 injections, 0.1mL each) in the second leg adding up to 16 injections of 80mg RZL-012 (1/3.125th the NOAEL based on HED from GLP toxicology study).

*based on HED from GLP toxicology

Cohort 2 - Lipedema		
Number of Subjects – Active	2	2
Total Dose RZL-012 (mg)	60	80
Dose per NOAEL*	1/4.688	1/3.125
Number of Injections	12	16

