**Induration — the measured local reaction at the greatest single diameter beyond the injected area surface of all injections (For Dercum's disease – nodules of 2-2.9 cm diameter 2*2 cm, nodules of 3-3.9 cm diameter 3*2 cm nodules of 4-8 cm diameter 4*2 cm. For lipedema -12*2 cm for the first subjects, 15*2cm for the following subjects and 16*2cm for the last subjects), the measurement should be recorded as a continuous variable.

Liver Enzyme Abnormalities Table

Serum *	Mild (Grade 1)	Moderate (Grade 2)	Severe (Grade 3)	Potentially Life Threatening (Grade 4)
Liver Function Tests –ALT, AST increase by factor	3 x ULN	3 – 5 x ULN	5-10 x ULN beyond 10 days	> 10 x ULN beyond 10 days

Study discontinuation is to be considered by the investigator in any case of an intolerable side effect and the actions taken are to be fully documented in source documents and Case Report Forms (CRFs).

To be considered an intolerable side effect, such an event must be considered to be possibly or probably related to the study drug.

Subjects experiencing an intolerable side effect will be withdrawn from the study, but followed for toxicity.

The study may also be prematurely terminated in any of the following cases:

- Recurring serious or severe ADR clinically evaluated by PI as warranting study termination.
- A decision made by Sponsor and/or IRBEC and/or local regulatory agency to terminate the study.

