5.3. SUBJECT IDENTIFICATION

A unique code numbers will be assigned by the investigator to the trial subject rather than the subjects' names, personal identification numbers, and/or addresses to protect the subject's identity. The code numbers and initials will be used in lieu of the subject's name when the investigator reports AEs and/or other trial related data.

5.4. REMOVAL, REPLACEMENT OR EARLY WITHDRAWAL OF SUBJECTS FROM ASSESSMENT NOT DUE TO INTOLERABLE SIDE EFFECTS

Subjects experiencing an intolerable side effect will be withdrawn from the study, but followed until the event resolves or becomes stable. If only one subject is withdrawn or removed from the study, and no more than one subject experience intolerable side effects, then the subject will not be replaced.

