6.2.6. Termination Visit

Once study is discontinued, all reasonable measures should be taken to perform a termination visit. Termination visit should include all procedures necessary to complete subjects' records: AE reporting, any clinical laboratory test needed to evaluate unresolved AEs, evaluation of response, recovery of all clinical supplies and compliance diaries, and updating of subject contact information. An effort should be made to perform all activities conducted on visit Day 28.

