7.3. PREMATURE DISCONTINUATION FROM STUDY

Study will be prematurely discontinued in any of the following cases:

- Subject's request.
- Any life-threatening (i.e., Grade 4) AE may cause premature discontinuation.
- Systemic hypersensitivity reaction may cause premature discontinuation.
- Any Grade 3 or 4 ADR (defined in Section 9.3) clinically evaluated by the PI and/or Sponsor as warranting subject discontinuation.
- Non-compliance: Subject's non-compliance with study procedures as evaluated by PI and/or Sponsor as warranting subject discontinuation.

- Other reasons regarded by PI as warranting subject's discontinuation.
- Premature study termination as described in Section 7.4.

Subjects who discontinue the study prematurely will be queried whether an AE contributed to their decision.

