10.5.2. Subject Disposition

A detailed description of subject accountability including count of subjects included, exposed, completed (i.e., subjects who complete the study treatment) and discontinued along with the main reason for discontinuation will be generated for each cohort and for all subjects. All withdrawals from the study, taking place on or after study drug injection, will be fully documented in the body of the Clinical Study Report.

Note that the actual study duration is for a period of maximum 2 months, with efficacy analyses being conducted at 28 days and 56 days.

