10.6. HANDLING OF MISSING DATA

No imputation of missing data will be performed.

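### Withdrawing subjects after an intolerable side effect stops no study drug but leaves their later scheduled visits unprotected, and the protocol disagrees with itself on whether withdrawal is mandatory

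*Protocol*

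**What the plan says.** On whether the subject leaves the study, the protocol gives two answers.

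- Mandatory: Section 3.3.2 has "Subjects experiencing an intolerable side effect will be withdrawn from the study, but followed for toxicity". Section 5.4 has "Subjects experiencing an intolerable side effect will be withdrawn from the study, but followed until the event resolves or becomes stable", and the synopsis entry defining an intolerable side effect says the same.
- Discretionary: Section 3.3.2 also has "Study discontinuation is to be considered by the investigator in any case of an intolerable side effect". Section 7.3 lists a Grade 3 or 4 adverse drug reaction as a reason only if "clinically evaluated by the PI and/or Sponsor as warranting subject discontinuation".

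On treatment, Section 3.3.1 says: "The dosing regimen will be a single dose treatment injection of RZL-012 in multiple sites". Section 6.2.3.1 places the injection at the baseline visit, Day 0.

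On what is measured later, Section 10.5.2 describes the study "with efficacy analyses being conducted at 28 days and 56 days". For missing values, Section 10.6 says "No imputation of missing data will be performed", and SAP Section 5.6 repeats this. Section 5.4 says that a single withdrawn subject is not replaced when no more than one subject has had an intolerable side effect.

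On what happens at withdrawal, Section 6.2.6 provides a termination visit and adds: "An effort should be made to perform all activities conducted on visit Day 28". Section 11.1 asks that final evaluations be attempted whatever the reason for withdrawal. Section 9.5.1 captures adverse events until the subject is terminated from the study, and Section 6.1.15 ties adverse event monitoring to participation, up to 56 days.

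**The concern.** In a repeated-dose trial, withdrawal for toxicity ends exposure. Here there is no later dose to withhold, so the practical effect of leaving the study is on data collection. The rule acts on the subjects with the worst reactions, so whether their later values are missing depends on the primary outcome.

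It is also linked to the secondary endpoints. Events that can count as intolerable include pain, skin or soft tissue inflammation and fat atrophy (Section 3.3.2). Severe local pain, tenderness and swelling are graded partly by whether they prevent daily activity. Local pain, function and fat reduction are what Section 4.2 sets out to measure. Day 28 and Day 56 summaries based on the subjects still attending could omit the worst pain and function results and, through fat atrophy, possibly the largest fat changes. The bias could run in either direction.

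The conflict in wording adds a second problem. The same event could lead to withdrawal or to continued attendance depending on which sentence is followed, so the amount of missing data is not fixed in advance.

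**Working it through.** **1. Mandatory or discretionary.** The two Section 3.3.2 sentences cannot both be operative if they concern the same decision. The discretionary one could be read as being about stopping the whole study. However, Section 7.3 uses discontinuation for subject-level reasons such as the subject's request and non-compliance, so the subject-level reading is the more natural one. The synopsis and Section 5.4 carry only the mandatory form.

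**2. Exposure.** There is one treatment, on Day 0. Study drug remaining to be stopped after that is zero.

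**3. What is covered after withdrawal and what is not.**

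| Item | Position in the documents |
|---|---|
| The intolerable event itself | Followed until resolved or stable (synopsis, 5.4) |
| Adverse drug reactions above Grade 1 | Followed to resolution or 6 months (9.5.1) |
| Serious adverse events | Reportable after injection, with no cut-off at withdrawal (9.5.2) |
| Safety and efficacy set membership | Kept: 10.4.1 names withdrawn subjects; 10.4.2 excludes only major violations at baseline |
| New non-serious adverse events | Capture ends when the subject is terminated (9.5.1) |
| Remaining scheduled labs, ECG and vital signs (to Day 28) and Draize scores (to Day 56) | Best-effort only (6.2.6, 11.1) |
| Day 28 ultrasound, circumference, pain, LEFS | Best-effort, on whatever day the termination visit falls (6.2.6) |
| Day 56 values of the same measures | Not named in 6.2.6; 11.1 sets no day |

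Circumference and LEFS apply to the lipedema cohort only. If withdrawal came in the first week, an ultrasound at the termination visit would be a first-week value. The SAP gives no rule assigning a termination visit to an analysis visit. Day 56 is the time point for duration of effect (6.1.16.2.3).

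**4. Size of one withdrawal.** The plan's own total is 6 + 6 = 12. It has no power calculation or dropout allowance behind it.

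- Cohort: 5 of 6 remain, and 1/6 = 16.7% is lost.
- Lipedema dose level, using the three-plus-three plan in the text of Section 3.3.1 and SAP Section 5.4.1: 2 of 3 remain, and 1/3 = 33.3% is lost.

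**5. Chance of at least one event.** The documents give no expected rate, so p is assumed, equal and independent across subjects. The formula is 1 − (1 − p)^n.

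| p | n = 6 | n = 12 |
|---|---|---|
| 5% | 1 − 0.735 = 26% | 1 − 0.540 = 46% |
| 10% | 1 − 0.531 = 47% | 1 − 0.282 = 72% |
| 20% | 1 − 0.262 = 74% | 1 − 0.069 = 93% |

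The rule for proceeding tolerates one affected subject, so by itself it does not change the chance of at least one.

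**6. Primary endpoint.** An event that triggers withdrawal is already counted. One in six gives 16.7% (exact 95% interval 0.4% to 64.1%) and one in twelve gives 8.3% (0.2% to 38.5%), whether or not the subject stays.

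**The case against.** A reader might infer that withdrawal loses the safety data of the most important cases, that it biases the primary endpoint, or that these subjects drop out of the efficacy set. The documents do not support any of these. An intolerable side effect is in general a drug reaction of Grade 3 or more, so it falls under the follow-up of reactions above Grade 1, well past Day 56 if needed. Serious events remain reportable, withdrawn subjects stay in the safety set, and the efficacy set definition already keeps them. The safety exposure that remains is narrower: new non-serious events, and scheduled tests not tied to the followed event.

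It is also fair to say that the probabilities describe the chance of an event, not of lost data. An event after Day 28 leaves the Day 28 values intact, and best-effort evaluations may recover others. Efficacy is secondary, uncontrolled and mainly descriptive. Individual listings are planned, and the study report must document every withdrawal after injection, so gaps would be visible. Declining to impute with six subjects per cohort is reasonable. These points limit the consequence. They do not supply the missing Day 56 values, and they do not settle the conflicting sentences.

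Finally, who should be discontinued after toxicity is a clinical matter. This point takes no position on it beyond asking for consistency.

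**Conclusion.** The concern holds in a limited form. The withdrawal texts in the synopsis and Sections 3.3.2, 5.4 and 7.3 conflict. Followed as written, the mandatory rule makes later missingness depend on the primary outcome without removing any study drug. The unprotected items are the Day 28 and Day 56 efficacy measures, new non-serious adverse events and the remaining scheduled safety tests.

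Each case puts one sixth of a cohort, or one third of a lipedema dose level, at risk at those visits. Under the assumed rates of 5% to 20%, at least one case among twelve subjects is roughly an even chance at the low end and near certain at the high end. No bias in any efficacy result has been quantified, and the documents give no basis for doing so.

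**What to change.** 1. Reconcile the synopsis with Sections 3.3.2, 5.4 and 7.3 so that they give one rule, and make clear whether the discretionary sentence in 3.3.2 concerns the subject or the study.
2. Separately from any decision on who is discontinued, state that subjects with an intolerable side effect continue all scheduled assessments and adverse event capture through Day 56 unless they withdraw consent. Align Sections 6.2.6 and 9.5.1 with this.

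No change to the analysis sets is needed.

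The cost is a protocol amendment, which Section 7.5 requires the sponsor and the IRB/EC to approve, and the completion of visits already on the schedule. The documents give no budget, so the expense of those visits cannot be stated.

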4. STUDY ENDPOINTS

4.1. PRIMARY ENDPOINTS

The primary endpoint will be the evaluation of the overall safety of RZL-012 injection into the subcutaneous fat in Dercum's disease and lipedema. The trial will proceed within a cohort provided that no more than one subject experiences intolerable side effects in a cohort.

4.2. SECONDARY ENDPOINTS

Following are the study's secondary endpoints:

1. For lipedema subjects - The reduction in local subcutaneous fat in the injection site region as compared to baseline as assessed by leg circumference above the knee assessments, see definition in Section 6.1.16.2.1 and by the reduction in nodules size and/or numbers assessed by ultrasound, see definition in Section 6.1.14.2.2.
2. For Dercum's disease subjects - The reduction in local subcutaneous fat in the injection site region as compared to baseline assessed by the reduction in nodules size and/or numbers by ultrasound, see definition in Section 6.1.14.2.2.
3. Extended duration of the fat reduction effect. To that end, ultrasound images and circumference measurement will be followed for 56 days, see definition in Section **Error! Reference source not found.**
4. Elucidation of the tissue changes by ultrasound of the injection site to include reduction in fat thickness and nodular quality, see definition in Section 6.1.16.2.4.
5. Improvement in local pain as measured by Comparative Pain Scale and by the reduction in the use of analgesics, see definition in Section 6.1.16.2.4.

6. Improvement in QOL and function in lipedema subjects as measured by questionnaire (such as The Lower Extremity Functional Scale (LEFS)), see definition in Section 6.1.16.2.5.

5. STUDY POPULATION

5.1. INCLUSION CRITERIA

Subjects meeting all of the following criteria will be eligible for study participation:

1. Post-menopausal (at least 2 years) women no more than 65 years old, with lipedema involving substantial fat above the knee or nodular Dercum's disease in such women and in men 20 - 65 years with nodular Dercum's disease.
2. For Dercum's disease subjects – at least 2 nodules to be injected of at least 2cm diameter each, as determined by ultrasound
3. For lipedema subjects - Significant subcutaneous fat above the knee as determined by circumference of 50cm
4. Generally considered healthy according to medical history, physical examination, ECG and laboratory evaluation with a special emphasis on metabolic parameters (fasting glucose concentration < 200 mg, normal blood pressure).
5. Subjects must be able to adhere to the visit schedule and protocol requirements and be available to complete the study.
6. Subjects must sign an informed consent indicating that they are aware of the investigational nature of the study.

5.2. EXCLUSION CRITERIA

Subjects meeting any of the following criteria will be excluded:

1. Unable to tolerate subcutaneous injection.
2. Subjects with uncontrolled cardiac, hepatic, renal or neurologic/psychiatric disorders, that in the opinion of the investigator, put the subject at significant risk, are not eligible.
3. Positive blood screen for Hepatitis B surface antigen (HbSAg), Hepatitis C virus (HCV), or Human immunodeficiency virus (HIV), or positive urine screen for alcohol or drugs of abuse (unless prescribed by a physician).
4. Subjects with a clinical history of primary or secondary immunodeficiency, autoimmune disease or subjects taking immunosuppressive drugs such as corticosteroids are ineligible.
5. As a result of medical review, physical examination, the PI (or medically qualified nominee) considers the subject unfit for the study.
6. Known sensitivity to components of the injection formulation.
7. Prior wound, tattoo or infection in the treated area.

8. Prior invasive treatment such as surgery or injectable drug at the RZL-012 injected area.

5.3. SUBJECT IDENTIFICATION

A unique code numbers will be assigned by the investigator to the trial subject rather than the subjects' names, personal identification numbers, and/or addresses to protect the subject's identity. The code numbers and initials will be used in lieu of the subject's name when the investigator reports AEs and/or other trial related data.

5.4. REMOVAL, REPLACEMENT OR EARLY WITHDRAWAL OF SUBJECTS FROM ASSESSMENT NOT DUE TO INTOLERABLE SIDE EFFECTS

Subjects experiencing an intolerable side effect will be withdrawn from the study, but followed until the event resolves or becomes stable. If only one subject is withdrawn or removed from the study, and no more than one subject experience intolerable side effects, then the subject will not be replaced.

6. STUDY PROCEDURES AND ASSESSMENT

6.1. DEFINITIONS OF STUDY PROCEDURES

6.1.1. Informed Consent

Prior to initiation of any study procedures, each subject will undergo an Informed Consent process in which the subject voluntarily confirms their willingness to participate in the trial, after having been informed of all aspects of the trial relevant to their decision to participate. The investigator, or a person designated by the investigator, will fully inform the subject of all pertinent aspects of the trial. In addition, the investigator, or a person designated by the investigator, will inform the subject that he is free to refuse to enter the study or to withdraw from the study at any time, for any reason.

The Informed Consent Form (ICF) approved by the IRB/EC will contain a description of the study's purpose, procedures, inconveniences and potential risks, and anticipated benefits.

Prior to a subject's participation in the trial, an ICF will be signed and personally dated by the subject and by the person who conducted the Informed Consent discussion.

If a subject is unable to read, he may not participate in the study.

Prior to participation in the trial, the subject will receive a copy of the signed and dated written ICF. During participation in the trial, the subject will receive a copy of the signed and dated consent form updates and a copy of any amendments to the written information provided to subjects.

The investigator should document in the source data that the Informed Consent was signed prior to subject's participation in the study and according to the International Conference on Harmonization Good Clinical Practice (ICH-GCP) guidelines, as described above.

6.1.2. Medical History

Subjects' medical history should be fully documented at Screening Day (14 through 2 days prior to baseline), to ensure compliance with study inclusion criteria and the absence of circumstance mentioned in the exclusion criteria. Medical history information must include, but not be limited to, past and present medical conditions, concomitant non-drug treatments and hypersensitivity to drugs.

6.1.3. Concomitant Medication

All concomitant medication given 1 month prior to study entry, including blood and blood products, dietary supplements, and non-prescription drugs will be listed at screening/baseline. Each entry will include the treatment's start date, treatment name (Generic), reason for use, dosing regimen (dose and frequency of use), route of administration, and stop date (if applicable). The clinical significance of the medication use will be decided by the investigator. Study subjects will be routinely questioned for changes in the administration of concomitant medication during the trial and changes should be updated from medical records as well.

6.1.4. Physical Examination

The investigator (or medically qualified nominee) will conduct a complete physical examination, height and weight measurements at Screening Day (performed 14 through 2 days prior to baseline). Clinically significant abnormal findings except overweight and obesity should be discussed with the Sponsor.

Additional physical examination to assess subject's safety and weight measurement will be performed on study visit on Day 28.

6.1.5. Pain Measurement

Local pain as measured by Comparative Pain Scale (Appendix II) will be measured at Screening Day (performed 14 through 2 days prior to baseline) in order to establish a baseline to compare following drug injection. For lipedema subjects Comparative Pain Scale will be measured for each leg and for Dercum's disease subjects for each selected lipoma for injection.

Additional pain measurements will be performed on study visits Day 14, 28, and 56.

Pain will be also assessed by Subject's self-recording the daily use of analgesics in a diary. Subjects will receive a diary on Screening Day and will start recording daily painkiller use along the trial till Day 28. A week before Day 56 visit, subjects will record their daily use of

analgesics. Diaries will be checked routinely on each study visit and data will be captured in the CRFs.

6.1.6. Quality of Life and Function Measurement

QOL and function assessed by the LEFS questionnaire (Appendix III) will be measured in lipedema subjects at Screening Day (performed 14 through 2 days prior to baseline) in order to establish a baseline to compare following drug injection.

Additional pain measurements will be performed on study visits Day 14, 28 and 56.

